## 7.3. Efficacy

Efficacy of sirukumab in GCA will be assessed from the presence of GCA activity including investigator assessment of signs and symptoms of GCA (new onset localized headache, scalp or temporal artery tenderness, reduced or absent pulsation in temporal artery, cord-like thickening of temporal artery, stroke, scalp necrosis, pain over face/scalp arteries, or otherwise unexplained mouth or jaw pain upon mastication [i.e., jaw claudication]); visual signs and symptoms (including but not limited to transient or episodic blurry vision, diplopia, scotoma, ischemia-related vision loss [permanent vision loss due to AION], amaurosis fugax); PMR symptoms [shoulder and/or hip girdle pain associated with inflammatory stiffness]; other features associated with GCA such as new or worsened extremity claudication and fever of unknown origin; and laboratory results for serum ESR and CRP levels (blinded to investigator).

### **7.3.1. Patient's and Physician's Global Assessment of Disease Activity**

The Patient's and Physician's Global Assessments of Disease Activity will be recorded on a VAS. The scale for the subject's assessment ranges from "very well" to "very poor". The scale for the physician's assessment ranges from "no GCA activity" to "extremely active GCA". The evaluating physician and subject must complete the global assessment independently of each other. The physician should preferably be the same person at every study visit for a given subject.

## **7.4. Health Outcomes**

In addition to the Patient's and Physician's Global Assessment of Disease Activity, other health outcome measures used in this study are PGIC, pain assessment using an 11-point numeric rating scale, HAQ-DI, FACIT-fatigue, Steroid Impact questionnaire, SF-36 v2 Acute health survey questionnaire, and EQ5D (5L). These questionnaires should be completed in the order specified in Section 7.

### **7.4.1. Patient Global Impression of Change (PGIC)**

Patient-reported response to treatment will be assessed using the Patient Global Impression of Change (PGIC) measure, a single item completed by subjects to provide a clinically meaningful summary of an individual's response to treatment. The assessment provides an estimate of the magnitude of treatment response at different time points during the study. Additionally, the subject rating of change will be used to support the estimation of a minimum clinically meaningful change score for the Steroid Impact PRO. Responses include: Much Better, Better, Slightly Better, No Change, Slightly Worse, Worse, Much Worse.

### **7.4.2. Pain Assessment**

Subjects will be asked to rate the severity of their average pain now on an 11-point numeric rating scale with anchors ranging from 0, "no pain" to 10, "the worst pain imaginable".

### **7.4.3. Health Assessment Questionnaire – Disability Index (HAQ-DI)**

The functional status of the subgroup of subjects with PMR will be assessed using the HAQ-DI [Fries, 1980]. This 20-question instrument assesses the degree of difficulty encountered in accomplishing tasks in 8 functional areas (dressing, arising, eating, walking, hygiene, reaching, gripping, and activities of daily living). Responses are scored from 0 (no difficulty) to 3 (inability to perform a task in that area).

#### **7.4.4. Functional Assessment of Chronic Illness Therapy-Fatigue (FACIT-Fatigue)**

The FACIT-Fatigue is a questionnaire that assesses self-reported tiredness, weakness, and difficulty conducting usual activities due to fatigue [Cella, 2002; Yellen, 1997]. The total FACIT-Fatigue score ranges from 0 to 52, with a higher score indicating less fatigue.

#### **7.4.5. Steroid Impact Questionnaire**

The benefits, side effects and impact of steroids on GCA symptoms and subjects will be assessed using a GCA disease specific patient reported questionnaire, the Steroid Impact Questionnaire. The Steroid Impact Questionnaire contains 50 items assessing steroid dose/duration (4 items), general impact (baseline burden; 19 items), benefits (7 items), work/productivity (3 items), side effects (10 items), emotions (6 items), and overall satisfaction (1 item).

#### **7.4.6. 36-item Short Form Version 2 Acute (SF-36v2 Acute)**

The Medical Outcome Study health measure entitled the 36-item Short-Form Version 2 acute (SF-36v2 acute) health survey questionnaire was developed as part of the Rand Health Insurance Experiment and consists of 8 multi-item scales.

- Limitations in physical functioning due to health problems.
- Limitations in usual role activities due to physical health problems.
- Bodily pain.
- General mental health (psychological distress and well-being).
- Limitations in usual role activities due to personal or emotional problems.
- Limitations in social functioning due to physical or mental health problems.
- Vitality (energy and fatigue).
- General health perception.

These scales are scored from 0 to 100 with higher scores indicating better health. Another algorithm yields 2 summary scores, the Physical Component Score (PCS) and Mental Component Score (MCS). These summary scores are also scaled with higher scores indicating better health [Ware, 1994]. The concepts measured by the SF-36 are not specific to any age, disease, or treatment group, allowing comparison of relative burden of different diseases and the relative benefit of different treatments [Ware, 1992].

#### **7.4.7. EuroQoL-5D (EQ-5D) (5L)**

The EQ-5D is a standardized measure of health status developed by the EuroQoL Group to provide a simple, generic measure of health for clinical and economic appraisal (EuroQol Group, 1990). The EQ-5D is applicable to a wide range of health conditions

and treatments. EQ-5D essentially consists of 2 elements: The EQ-5D descriptive system and the EQ visual analogue scale (EQ VAS). The EQ-5D descriptive system comprises the following 5 dimensions: mobility, self-care, usual activities, pain/discomfort and anxiety/depression. Each dimension has 5 levels: no problems, slight problems, moderate problems, severe problems, unable to do. The respondent is asked to indicate his/her health state by ticking (or placing a cross) in the box against the most appropriate statement in each of the 5 dimensions. This decision results in a 1-digit number expressing the level selected for that dimension. The digits for 5 dimensions can be combined in a 5-digit number describing the respondent's health state which can be converted into a single summary index (EQ-5D index) by applying a formula that attaches values (also called weights) to each of the levels in each dimension. The EQ VAS records the respondent's self-rated health on a vertical line, VAS where the endpoints are 'Best imaginable health state' and 'Worst imaginable health state'. The EQ VAS can be used as a quantitative measure of health outcome as judged by the individual respondents.

## **7.5. Safety**

Safety will be assessed from the documentation of adverse events and review of vital signs and laboratory assessments including complete blood counts, serum chemistry profiles, fasting serum lipids, HbA1c, hepatitis B and C serologies, and markers of bone turnover. The Columbia-Suicide Severity Rating Scale (C-SSRS) will be used to prospectively monitor suicidal ideation and behavior (Section 7.5.7). Adverse events (including serious and opportunistic infections, cardiovascular events, gastrointestinal perforations, hepatic laboratory abnormalities, and cytopenias) will be monitored on a regular and/or event-driven basis by an IDMC throughout the study.

Planned time points for all safety assessments are listed in the Time and Events Tables (Section 7.1).

### **7.5.1. Adverse Events (AE) and Serious Adverse Events (SAEs)**

The definitions of an AE or SAE can be found in [Appendix 4](#).

The investigator and their designees are responsible for detecting, documenting and reporting events that meet the definition of an AE or SAE.

#### **7.5.1.1. Time period and Frequency for collecting AE and SAE information**

- AEs and SAEs will be collected from the start of Study Treatment until the follow-up contact (see Section 7.5.1.3), at the time points specified in the Time and Events Tables (Section 7.1).
- Medical occurrences that begin prior to the start of study treatment but after obtaining informed consent may be recorded on the Medical History/Current Medical Conditions section of the CRF.

- Any SAEs assessed as related to study participation (e.g., protocol-mandated procedures, invasive tests, or change in existing therapy) or related to a GSK product will be recorded from the time a subject consents to participate in the study up to and including any follow-up contact.
- All SAEs will be recorded and reported to GSK within 24 hours, as indicated in [Appendix 4](#).
- Investigators are not obligated to actively seek AEs or SAEs in former study subjects. However, if the investigator learns of any SAE, including a death, at any time after a subject has been discharged from the study, and he/she considers the event reasonably related to the study treatment or study participation, the investigator must promptly notify GSK.

NOTE: The method of recording, evaluating and assessing causality of AEs and SAEs plus procedures for completing and transmitting SAE reports to GSK are provided in.

#### **7.5.1.2. Method of Detecting AEs and SAEs**

Care will be taken not to introduce bias when detecting AEs and/or SAEs. Open-ended and non-leading verbal questioning of the subject is the preferred method to inquire about AE occurrence. Appropriate questions include:

- “How are you feeling?”
- “Have you had any (other) medical problems since your last visit/contact?”
- “Have you taken any new medicines, other than those provided in this study, since your last visit/contact?”

#### **7.5.1.3. Follow-up of AEs and SAEs**

After the initial AE/SAE report, the investigator is required to proactively follow each subject at subsequent visits/contacts. All SAEs, and non-serious AEs of special interest (as defined in Section [4.6.1](#)) will be followed until resolution, until the condition stabilizes, until the event is otherwise explained, or until the subject is lost to follow-up (as defined in Section [5.4](#)). Further information on follow-up procedures is given in [Appendix 4](#).

Other AEs of special interest not defined in Section [4.6.1](#) are injection site reactions, total or partial blindness, limb claudication, and scalp or tongue necrosis. In addition, severe disease flares, including hospitalizations will be monitored.

Other AEs of special interest for sirukumab are hematologic laboratory abnormalities (decreases in neutrophils and platelets), hepatobiliary laboratory abnormalities, lipid parameter abnormalities, serious CV events, infections, malignancies, and gastrointestinal perforations.

All initial reports of cardiovascular AEs (myocardial infarction, stroke, death, hospitalization for angina, hospitalization for TIA), newly identified malignancies, active TB, hepatobiliary abnormalities (as defined below), and gastrointestinal perforations

must be reported to the Sponsor by the investigational staff within 24 hours of their knowledge of the event even if these events do not meet the definition of an SAE.

Corticosteroid-related AEs such as diabetes mellitus, osteoporosis, fractures, infection, glaucoma, and cataracts among others will be evaluated in relation to steroid exposure and baseline risk. Since subjects participating in this study may be receiving high doses of prednisone for a prolonged period, investigators should consider implementation of the American College of Rheumatology recommendations for the prevention and treatment of glucocorticoid-induced osteoporosis (Grossman, 2010). A summary of these recommendations is included in Section 12.5, Appendix 5. Investigators should also consider whether their subjects may benefit from other approaches for minimizing corticosteroid-related AEs, such as the prophylactic use of proton pump inhibitors for gastroprotection.

#### **7.5.1.4. Cardiovascular and Death Events**

For any cardiovascular events detailed in Appendix 4 and all deaths, whether or not they are considered SAEs, specific Cardiovascular (CV) and Death sections of the CRF will be required to be completed. These sections include questions regarding CV (including sudden cardiac death) and non-CV death.

The CV CRFs are presented as queries in response to reporting of certain CV MedDRA terms. The CV information should be recorded in the specific cardiovascular section of the CRF within one week of receipt of a CV Event data query prompting its completion.

The Death CRF is provided immediately after the occurrence or outcome of death is reported. Initial and follow-up reports regarding death must be completed within one week of when the death is reported.

In the sirukumab clinical programs, significant changes in lipid laboratory parameters have been observed, as with other agents that block IL-6. The clinical significance of these changes is not known. Nonetheless, serious CV events are considered AEs of special interest and will be closely monitored in the sirukumab program. In order to fully understand CV events in this study, Major Adverse Cardiovascular Events (MACE), defined as myocardial infarction, stroke, death, hospitalization for unstable angina, and hospitalization for TIA, will be collected and prospectively adjudicated by an external CEC. The CEC is an independent committee composed of external specialists, blinded to treatment assignment, who will be commissioned to review case information on serious CV events. This will allow external review of cases and determination of diagnosis prior to analysis.

#### **7.5.1.5. Other Adverse Events of Special Interest for Sirukumab**

##### **Laboratory parameter abnormalities**

IL-6 is a pleiotropic cytokine necessary for hematopoiesis and IL-6 inhibition has been shown to cause a reduction in both neutrophils and platelets. In addition, IL-6 inhibition has been associated with reversible elevation in liver enzymes. Mechanisms by which

this might occur include inhibition of the hepatoprotective effect of IL-6, leaving hepatocytes susceptible to effects of toxins and other stresses. Lipid abnormalities have also been observed, both in the sirukumab Phase 2 study C1377T04, as well as with other anti-IL-6 agents. The mechanism by which this occurs is not fully understood.

### **Other Events of Interest**

Sirukumab, by its mechanism of action as an IL-6 inhibitor, would be expected to have some properties of immunosuppression. Increased susceptibility to infections is an identified risk of sirukumab. Serious, life-threatening infections such as septic shock, some of which have been fatal, have occurred in subjects receiving sirukumab. IL-6 deficient mice have been found to be susceptible to infections with *Listeria monocytogenes*, *Toxoplasma gondii*, and *Candida albicans*. [Dalrymple, 1995; Romani, 1996; Suzuki, 1997]. In addition, as an IL-6 inhibitor, sirukumab may have some effect on the risk of malignancy by affecting immune surveillance. Further, gastrointestinal perforations have been reported with another anti-IL-6 agent [ACTEMRA Prescribing Information, 2011] and with sirukumab. Please refer to Table 4.6.1 and the Investigator Brochure for additional information.

### **7.5.1.6. Events That Occur With Biologics**

#### **Injection Site Reactions**

An injection site reaction is any unfavorable or unintended sign that occurs at the study drug injection site. All subjects must be carefully observed for symptoms of an injection site reaction. Prior to and including through Week 4, subjects will be observed for at least 30 minutes after the SC injection of study drug for symptoms of an injection site reaction. After Week 4, subjects do not need to be observed for 30 minutes for the post-administration injection-site evaluation if they are self-administering at home. However, subjects should promptly notify the site if they experience a reaction at the site of injection. If an injection site reaction is observed, the subject should be treated at the investigator's discretion. Any adverse reaction (eg, pain, erythema, and/or induration) should be noted on the AE page of the eCRF.

#### **Allergic/Hypersensitivity Reactions**

All subjects will be observed carefully for symptoms of allergic reactions for at least 30 minutes after the SC injection of study drug when administered at the study site. If mild or moderate allergic reaction is observed, acetaminophen 650 mg per mouth (PO) or NSAIDS and diphenhydramine 25 mg orally or intravenously may be administered. If the reaction is not severe, subsequent injections at the appropriate treatment intervals may be undertaken with caution.

Subjects with severe reactions following an injection such as bronchospasm with wheezing and/or dyspnea requiring ventilator support, or symptomatic hypotension with a decrease in systolic blood pressure greater than 40 mmHg will not be permitted to receive any additional study drug injections. In the case of such reactions, appropriate medical treatment should be administered.

In cases of serious allergic/hypersensitivity reactions, additional details on the case will be collected via a targeted follow-up questionnaire. An internal safety review team will adjudicate these events to determine if the events meet the Sampson criteria ([Sampson, 2006](#)).

#### **7.5.1.7. Regulatory Reporting Requirements for SAEs**

Prompt notification by the investigator to GSK of SAEs and non-serious AEs related to study treatment (even for non- interventional post-marketing studies) is essential so that legal obligations and ethical responsibilities towards the safety of subjects and the safety of a product under clinical investigation are met.

GSK has a legal responsibility to notify both the local regulatory authority and other regulatory agencies about the safety of a product under clinical investigation. GSK will comply with country specific regulatory requirements relating to safety reporting to the regulatory authority, Institutional Review Board (IRB)/Independent Ethics Committee (IEC) and investigators.

Investigator safety reports are prepared for suspected unexpected serious adverse reactions according to local regulatory requirements and GSK policy and are forwarded to investigators as necessary.

An investigator who receives an investigator safety report describing a SAE(s) or other specific safety information (e.g., summary or listing of SAEs) from GSK will file it with the IB and will notify the IRB/IEC, if appropriate according to local requirements.

#### **7.5.2. Pregnancy**

- Details of all pregnancies in female subjects and female partners of male subjects will be collected after the start of dosing and until the Follow-up visit.
- If a pregnancy is reported then the investigator should inform GSK within 2 weeks of learning of the pregnancy and should follow the procedures outlined in [Appendix 2](#).
- Female subjects who become pregnant during the study must have study drug discontinued immediately. These subjects should continue to follow the protocol-specified visit schedule.

#### **7.5.3. Physical Exams**

- A complete physical examination will be conducted at screening and will include, at a minimum, assessment of the Cardiovascular, Respiratory, Gastrointestinal and Neurological systems. Height and weight will also be measured and recorded.
- A brief physical examination will be conducted at all other time points and include, at a minimum assessments of the skin, lungs, CV system, and abdomen (liver and spleen).

- Investigators should pay special attention to clinical signs related to previous serious illnesses.

#### **7.5.4. Vital Signs**

Vital signs will be measured in semi-supine position after 5 minutes rest and will include temperature, systolic and diastolic blood pressure and pulse rate.

#### **7.5.5. Electrocardiogram (ECG)**

Triplicate 12-lead ECGs will be obtained at the Screening visit using an ECG machine that automatically calculates the heart rate and measures PR, QRS, QT, and QTc intervals. The screening ECG will ensure that a comparative ECG is available prior to study drug administration in order to detect any changes should a subject require an ECG for any reason during the study. Refer to Section 5.4.4 for QTc discontinuation criteria and additional QTc readings that may be necessary.

In the event of a suspected cardiac abnormality, the investigator should make every reasonable attempt to obtain the results of the ECG performed in the emergency hospital facility.

#### **7.5.6. Clinical Safety Laboratory Assessments**

All protocol required laboratory assessments, as defined in [Table 6](#), must be conducted in accordance with the Laboratory Manual, and Protocol Time and Events Schedules. Laboratory requisition forms must be completed and samples must be clearly labelled with the subject number, protocol number, site/centre number, and visit date. Details for the preparation and shipment of samples will be provided by the laboratory and are detailed in the laboratory manual. Reference ranges for all safety parameters will be provided to the site by the laboratory responsible for the assessments.

Pregnancy testing (where applicable) should be conducted every 4 weeks while subjects are receiving study drug and during the 16-week follow-up period. Pregnancy tests may be performed by the subject at home using the test kits provided by the central laboratory when there is no study visit associated with the testing time point.

If additional non-protocol specified laboratory assessments are performed at the institution's local laboratory and result in a change in subject management or are considered clinically significant by the investigator (e.g., SAE or AE or dose modification) the results must be recorded in the CRF.

Hematology, clinical chemistry, and additional parameters to be tested are listed in [Table 6](#).

All laboratory tests with values that are considered clinically significantly abnormal during participation in the study or within 112 days after the last dose of study treatment should be repeated until the values return to normal or baseline. If such values do not

return to normal within a period judged reasonable by the investigator, the etiology should be identified and the sponsor notified.

The National Cancer Institute Common Terminology Criteria for Adverse Events (NCI-CTCAE) will be used to grade laboratory abnormalities as appropriate.

The investigators and the Sponsor/study team will remain blinded to the results of the ESR (performed locally), CRP and fasting lipid analyses (see Section 6.4) after the start of treatment during Part A of the study. The central laboratory will send an alert to the investigator for LDL values >160 mg/dL (SI units 4.1 mmol/L) or triglycerides >500 mg/dL (SI units 5.6 mmol/L).

**Table 6 Laboratory Parameters**

Hematology		
Hemoglobin	Hematocrit	Red blood cell (RBC) count
White blood cell (WBC) count with differential	Neutrophils, absolute	Neutrophils, segs (%)
Neutrophils, bands (%)	Basophils (%)	Eosinophils (%)
Eosinophils, absolute	Lymphocytes (%)	Monocytes (%)
Platelet count		
Serum Chemistry		
Sodium	Potassium	Chloride
Bicarbonate	Blood urea nitrogen (BUN)	Creatinine
Glucose	Aspartate transaminase	Alanine transaminase
Alkaline phosphatase	Calcium	Phosphate
Albumin	Total protein	Bilirubin, direct, indirect and total
Fasting lipids		
Total cholesterol	Low density lipoprotein (LDL)	High density lipoprotein (HDL)
Triglycerides		
Serum and urine pregnancy test for premenopausal women only		
Serology for HIV, hepatitis B surface antigen, hepatitis B core antibody and hepatitis C antibody 		
Other tests		
Hemoglobin A1c	C-reactive protein (CRP) 	Erythrocyte sedimentation rate (ESR) 
QuantIFERON-TB Gold Test		

1. If hepatitis C antibody positive, a hepatitis C RNA PCR assay should be reflexively performed on a fresh sample to confirm the result
2. Investigators will remain blinded to the results of the ESR, CRP and fasting lipids after the start of treatment during Part A of the study (see Section 6.4). ESR will be analyzed at the local laboratory.
3. Required for the evaluation of efficacy.

Values for liver transaminase levels (AST, ALT), absolute neutrophil count (ANC), and platelet count that require study drug interruption and/or permanent discontinuation of study drug administration are listed below in [Table 7](#).

**Table 7 Values for Liver Transaminase Levels, Absolute Neutrophil Count, and Platelet Count That Require Study Drug Interruption and/or Permanent Discontinuation of Study Drug**

ALT or AST increased	
ALT or AST	Action
≥3xULN) for laboratory reference range.	Interrupt study drug administration, assess for symptoms, and repeat ALT/AST test as soon as possible* (see Section 5.4.3). May resume study drug when <3x ULN
Criteria for drug-induced liver injury	Permanent discontinuation of study drug
Low Absolute Neutrophil Count (ANC)	
Neutrophil count	Action
0.5 to ≤1.0 x 10  /μL (SI: 0.5 to ≤1.0 x 10  cells/L)	Interrupt study drug administration, repeat ANC test as soon as possible* May resume study drug when >1.0 x 10  /μL
<0.5 x 10  /μL (SI: <0.5 x 10  cells/L)	Interrupt study drug administration, repeat ANC test as soon as possible* If confirmed to be <0.5 x 10  /μL, discontinue study drug permanently (see Section 5.4.2)
Low Platelet Count	
Platelet count	Action
50,000 to ≤100,000/μL (SI: 50 to ≤100 x 10  cells/L)	Interrupt study drug administration, repeat platelet count test as soon as possible* May resume study drug when platelet count >100,000/μL
<50,000/μL (SI: <50 x 10  cells/L)	Interrupt study drug administration, repeat platelet count test as soon as possible* If confirmed to be <50,000/μL, discontinue study drug permanently (see Section 5.4.2)

\* Retesting should be performed by Central laboratory

Note: A WBC evaluation may include any abnormal cells, which will then be reported by the laboratory. Any RBC evaluation may include abnormalities in the RBC count and/or RBC parameters and/or RBC morphology, which will then be reported by the laboratory. In addition, any other abnormal cells in a blood smear will also be reported.

Any abnormalities in MCH, MCHC and MCV will be reported by the laboratory.

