#### **5.4.3. Liver Chemistry Stopping Criteria**

**Liver chemistry stopping and increased monitoring criteria** have been designed to assure subject safety and evaluate liver event etiology (in alignment with the FDA premarketing clinical liver safety guidance).  
<http://www.fda.gov/downloads/Drugs/GuidanceComplianceRegulatoryInformation/Guidances/UCM174090.pdf>

[figure not shown]
Subjects meeting the liver chemistry stopping and increased monitoring criteria may be required to temporarily or permanently discontinue study treatment.

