**Phase III-IV Liver Chemistry Increased Monitoring Algorithm with Continued Therapy for ALT  $\geq 3xULN$  but < 8xULN**

Liver Safety Required Actions and Follow up Assessments Section can be found in [Appendix 3](#)

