#### 5.4.3.1. Study Treatment Restart or Rechallenge

Study treatment restart or rechallenge after liver chemistry stopping criteria are met by any subject participating in this study is not allowed.

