#### Phase III-IV liver chemistry stopping criteria and required follow up assessments

Liver Chemistry Stopping Criteria - Liver Stopping Event	
ALT-absolute	ALT $\geq$ 8xULN
ALT Increase	ALT $\geq$ 5xULN but <8xULN persists for $\geq$ 2 weeks ALT $\geq$ 3xULN but <5xULN persists for $\geq$ 4 weeks
Bilirubin	ALT $\geq$ 3xULN and bilirubin $\geq$ 2xULN (>35% direct bilirubin)
INR^2	ALT $\geq$ 3xULN and INR>1.5, if INR measured
Cannot Monitor	ALT $\geq$ 5xULN but <8xULN and cannot be monitored weekly for $\geq$ 2 weeks ALT $\geq$ 3xULN but <5xULN and cannot be monitored weekly for $\geq$ 4 weeks
Symptomatic	ALT $\geq$ 3xULN associated with symptoms (new or worsening) believed to be related to liver injury or hypersensitivity
Required Actions and Follow up Assessments following ANY Liver Stopping Event	
Actions	Follow Up Assessments

 
Immediately discontinue study treatment
 
Report the event to GSK within 24 hours
 
Complete the liver event CRF and complete an SAE data collection tool if the event also meets the criteria for an SAE
 
Perform liver event follow up assessments
 
Monitor the subject until liver chemistries resolve, stabilize, or return to within baseline (see MONITORING below)
 
	
 
Viral hepatitis serology
 
Only in those with underlying chronic hepatitis B at study entry (identified by positive hepatitis B surface antigen) quantitative hepatitis B DNA and hepatitis delta antibody.
 
Blood sample for PK analysis, obtained within 24 hours after last dose
 
Serum creatine phosphokinase (CPK) and lactate dehydrogenase (LDH).
 

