### Phase III-IV liver chemistry increased monitoring criteria with continued therapy

Liver Chemistry Increased Monitoring Criteria – Liver Monitoring Event	
Criteria	Actions

ALT <math>\geq</math>5xULN and <8xULN and bilirubin <2xULN without symptoms believed to be related to liver injury or hypersensitivity, and who can be monitored weekly for 2 weeks.
 
OR
 
ALT <math>\geq</math>3xULN and <5xULN and bilirubin <2xULN without symptoms believed to be related to liver injury or hypersensitivity, and who can be monitored weekly for 4 weeks.
	
 
• Notify the GSK medical monitor within 24 hours of learning of the abnormality to discuss subject safety.
 
• Subject can continue study treatment
 
• Subject must return weekly for repeat liver chemistries (ALT, AST, alkaline phosphatase, bilirubin) until they resolve, stabilise or return to within baseline
 
• If at any time subject meets the liver chemistry stopping criteria, proceed as described above
 
• If ALT decreases from ALT <math>\geq</math>5xULN and <8xULN to <math>\geq</math>3xULN but <5xULN, continue to monitor liver chemistries weekly.
 
• If, after 4 weeks of monitoring, ALT <3xULN and bilirubin <2xULN, monitor subjects twice monthly until liver chemistries normalize or return to within baseline.
 

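### Table 7 requires the SC drug to be held at ALT 3 to <8×ULN, but Appendix 3 lets dosing continue in an asymptomatic subject in that band

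*Protocol*

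**What the plan says.** **Section 7.5.6 and Table 7.** The lead-in says that the table gives the transaminase and neutrophil values and "platelet count that require study drug interruption and/or permanent discontinuation of study drug administration are listed below". In the row for ALT or AST of 3×ULN or more, the action is "Interrupt study drug administration, assess for symptoms, and repeat ALT/AST test as soon as possible". Dosing may resume once the value is below 3×ULN. The row refers the reader to Section 5.4.3.

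**Section 5.4.3.** One of its two algorithm figures is headed "Liver Chemistry Increased Monitoring Algorithm with Continued Therapy for ALT" from 3×ULN to below 8×ULN, and points to Appendix 3. The running text says: "Subjects meeting the liver chemistry stopping and increased monitoring criteria may be required to temporarily or permanently discontinue study treatment". Section 5.4.3.1 adds: "Study treatment restart or rechallenge after liver chemistry stopping criteria are met by any subject participating in this study is not allowed".

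**Appendix 3 (Section 12.3).** The increased-monitoring table covers two ALT bands: 5 to <8×ULN with weekly monitoring possible for 2 weeks, and 3 to <5×ULN with weekly monitoring possible for 4 weeks. Both require bilirubin <2×ULN and no symptoms of liver injury or hypersensitivity. The listed actions include "Subject can continue study treatment", weekly liver tests, and notifying the medical monitor within 24 hours "of learning of the abnormality to discuss subject safety".

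**The concern.** The value in question is foreseeable. The risk table in Section 4.6.1 describes transient, asymptomatic transaminase rises with sirukumab, some of them above 5×ULN but below 8×ULN. A site that sees such a value needs one answer on whether the next two-weekly injection is given, particularly as subjects may inject at home between visits.

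Two sites could treat the same ALT value differently, each relying on protocol text. What is at stake is consistent safety conduct and, to a lesser degree, reporting. If the rise is recorded as an adverse event, it enters the SAP 9.1.6 table of events leading to interruption or delay of SC IP at a site that holds, but not at a site that doses on.

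**Working it through.** The check is a comparison of texts; the plan has no figure of its own to reproduce.

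**1. Same product.** Section 5.4.2 uses *study drug* for the blinded SC injection. Section 6.1 lets *study treatment* mean the individual products or their combination. The Appendix 3 permission therefore includes the SC injection, and the difference in terms does not separate the two rules.

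**2. Where the rules meet.**

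| Situation | Table 7 | Appendix 3 | Compatible? |
|---|---|---|---|
| ALT 3 to <8×ULN, bilirubin <2×ULN, no symptoms, weekly monitoring possible | Hold until below 3×ULN | Dosing may continue with weekly tests | No |
| ALT 3×ULN or more with symptoms, or with bilirubin 2×ULN or more (>35% direct) | Hold | Stop | Yes |
| ALT in the monitoring band beyond the persistence limit (for example "3xULN but <5xULN persists for" 4 weeks or more) | Hold | Stop | Yes |
| ALT 8×ULN or more | Hold | Stop | Yes |
| AST raised alone | Hold | No AST criterion | Yes; Table 7 alone applies |

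Only the first row conflicts, and it covers the whole ALT band from 3 to <8×ULN under the stated conditions.

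**3. Direction of the breach.** Table 7 is mandatory; Appendix 3 is permissive. A site that holds, notifies the medical monitor and tests weekly complies with both. A site that doses on complies with Appendix 3 and breaches Table 7.

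**4. Does any text set precedence?** Table 7 points to Section 5.4.3, whose sentence on discontinuation says *may be required* and so does not choose. The restart ban in 5.4.3.1 applies only after a stopping criterion is met, which is outside the disputed band.

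**5. Cost of a hold.** SAP 7.2.2.1 plans 11 injections for a last visit at Week 20, that is 20/2 + 1. On the same count, injections at Weeks 0 to 50 number 50/2 + 1 = 26. With one injection due every 2 weeks:
- 2-week hold: 1/26 = 3.8% of Part A injections
- 4-week hold: 2/26 = 7.7%

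**The case against.** The strongest defence is the discontinuation sentence in Section 5.4.3. Restart after a stopping event is banned, so its reference to temporary discontinuation fits the monitoring band best. That suggests the authors foresaw holds alongside continued therapy. The algorithm figures might also settle the matter, and the medical monitor hears of each case within 24 hours. These points stand as mitigation. However, the sentence is permissive, the visible heading of the relevant figure still speaks of continued therapy, and the monitor is not told which rule to apply.

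A reader might infer more than the documents support:

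- **That a site must break one rule or the other.** It need not: holding satisfies both.
- **That the six subjects in Section 4.6.1 with ALT or AST >3×ULN and bilirubin >2×ULN show the danger of dosing on.** The disputed band requires bilirubin <2×ULN, so they lie outside it.
- **That AST is also in conflict.** Appendix 3 has no AST criterion, so Table 7 governs it alone.
- **That the permanent-stop row of Table 7 is left without a definition.** Item 6 of Section 5.4.2 already requires permanent discontinuation for the liver abnormalities specified in Section 5.4.3, which leads to Appendix 3.
- **That the persistence limits cap the extra injections at a small fixed number.** Appendix 3 lets monitoring continue when ALT falls from the 5 to <8 band into the 3 to <5 band, so adding up each band's limit separately gives no valid maximum.
- **That responder status is materially affected.** SAP 4.6.1 does not count a temporary SC hold as permanent discontinuation, and SAP Section 8 now gives summary statistics only.

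It is also fair to say that the remedy comes late. The study was terminated on 10 October 2017 and early withdrawal visits were complete by 30 November 2017 (SAP 1.1).

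**Conclusion.** The protocol is inconsistent as written. In the defined ALT band, Table 7 requires a hold that Appendix 3 and a Section 5.4.3 heading treat as unnecessary, and no visible text says which governs. This is a safety-conduct and consistency problem, not a threat to the trial's efficacy inference. Its frequency cannot be sized, because the documents give no rate for ALT 3 to <8×ULN.

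The conclusion assumes that the missing Section 5.4.3 figures do not state a precedence. The injection percentages assume dosing at Weeks 0 to 50 and one scheduled injection in each 2 weeks of hold.

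**What to change.** Make the Table 7 hold the single rule, because it is already stated as a requirement and is the more cautious of the two.

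- In Appendix 3, replace the permission to continue with: *interrupt SC study drug, continue the prednisone taper, test weekly, and resume at <3×ULN unless a stopping criterion has been met*. Keeping the taper going matches what Section 5.4.2 says for temporary discontinuation.
- Change the *Continued Therapy* headings in Section 5.4.3 and Appendix 3 to match, and check the Section 5.4.3 figures against the new wording.

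The cost is one action line and two headings by protocol amendment. No visits are added, since Appendix 3 already calls for weekly tests. The downside is a few missed injections in subjects whose rise would have settled anyway: 1 of 26 for a 2-week hold, 2 of 26 for a 4-week hold.

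A column in the SAP 9.6.1 liver listing showing whether SC IP was held or continued is optional. The exposure (SAP 7.2.1), liver-event (9.6.1) and interruption (9.1.6) listings already largely show it.
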